## **3.3.2.** Benefit-Risk for Background Treatment

Proton pump inhibitors are FDA-approved for the short-term treatment in children for healing of EoE (CMS, 2013). A trial of PPIs prior to endoscopy with biopsy will ensure that pediatric patients with EoE who show improvement/resolution in their signs and symptoms of EoE with this treatment are appropriately excluded from this trial. Proton pump inhibitors are generally well tolerated, and risks associated with short-term use are minimal. The most common adverse reactions seen in pediatric patients are headache, diarrhea, constipation, and nausea. Chronic acid suppression can minimize the effectiveness of any medication requiring an acidic environment for absorption. Commonly prescribed medications affected by acid suppression are ampicillin esters, digoxin, atazanavir, ketoconazole, and iron salts.

# 4. **ENDPOINTS**

# 4.1. **Primary and Secondary Endpoints**

## 4.1.1. Primary Endpoint

• Proportion of patients achieving peak esophageal intraepithelial eosinophil count of ≤6 eos/hpf (400×) at week 16

#### 4.1.2. Secondary Endpoints

#### Secondary Efficacy Endpoints for Part A and B:

- Proportion of patients achieving peak esophageal intraepithelial eosinophil count of <15 eos/hpf at week 16
- Percent change in peak esophageal intraepithelial eosinophil count (eos/hpf) from baseline to week 16
- Absolute change in mean EoE grade score from the EoE-HSS from baseline to week 16
- Absolute change in mean EoE stage score from the EoE-HSS from baseline to week 16
- Absolute change in EoE EREFS from baseline to week 16
- Change from baseline in the type 2 inflammation transcriptional signature score at week 16
- Change from baseline to week 16 in the proportion of days with 1 or more EoE signs as measured by the Pediatric EoE Sign/Symptom Questionnaire-caregiver version (PESQ-C) (for patients aged ≥1 to <12 years)
- Number of sign-free days during the 14-day period preceding week 16 as measured by the PESQ-C (for patients aged ≥1 to <12 years)
- Change from baseline to week 16 in the proportion of total segments within a day (night, morning, afternoon, evening) with 1 or more EoE signs as measured by PESQ-C (for patients aged ≥1 to <12 years)
- Change from baseline to week 16 in the proportion of days with 1 or more EoE symptoms as measured by PESQ-P (patient version) (for patients aged  $\geq 8$  to <12 years)
- Number of symptom-free days during the 14-day period preceding week 16 as measured by the PESQ-P (patient version) (for patients aged ≥8 to <12 years)
- Change from baseline to week 16 in the proportion of total segments within a day (night, morning, afternoon, evening) with 1 or more EoE symptoms as measured by PESQ-P (for patients aged ≥8 to <12 years)
- Change in total score from baseline to week 16 as measured by the PEESSv2.0caregiver version questionnaire (for patients aged  $\geq 1$  to <12 years)
- Normalized Enrichment Scores (NES) for the relative change from baseline to week 16 in the EoE diagnostic panel (EDP) transcriptome signature
- NES for the relative change from baseline to week 16 in the type 2 inflammation transcriptome signature
- NOTE:
  - All the above primary and secondary endpoints (except for PEESSv2.0- caregiver version questionnaire) assessed at week 16 will be assessed at week 52 as secondary endpoints and summarized with descriptive statistics based on the

Regeneron Pharmaceuticals, Inc.

#### CONFIDENTIAL

treatment assignment in the double-blind treatment period as well as the extended active treatment assignment for patients previously in the placebo group.

- Change from baseline in body weight for age percentile at week 52
- Change in body mass index for age z-score from baseline to week 52 for patients ≥2 years of age
- Change in weight for age z-score from baseline to week 52
- Change in weight for height z-score from baseline to week 52

#### Secondary Efficacy Endpoints for Part C (open-label extension period) only:

- Proportion of patients achieving peak esophageal intraepithelial eosinophil count of ≤6 eos/hpf (400×) at week 100 and week 160
- Proportion of patients achieving peak esophageal intraepithelial eosinophil count of <15 eos/hpf at week 100 and week 160
- Percent change in peak esophageal intraepithelial eosinophil count (eos/hpf) from baseline to week 100 and week 160
- Absolute change in mean EoE grade score from the EoE-HSS from baseline to week 100 and week 160
- Absolute change in mean EoE stage score from the EoE-HSS from baseline to week 100 and week 160
- Absolute change in EoE-EREFS from baseline to week 100 and week 160
- Normalized Enrichment Scores (NES) for the relative change from baseline to week 100 and 160 in the EoE diagnostic panel (EDP) transcriptome signature
- NES for the relative change from baseline to week 100 and week 160 in the type 2 inflammation transcriptome signature
- Change in total score from baseline to week 160 as measured by the PEESSv2.0caregiver version questionnaire
- Proportion of patients (with food elimination diet regimens at baseline) that have a reintroduction of a previously eliminated food group by week 100 and by week 160
- Change from baseline in body weight for age percentile up to week 160
- Change in body mass index for age z-score for patients ≥2 years of age from baseline to up to week 160
- Change in weight for age z-score from baseline to up to week 160
- Change in weight for height z-score from baseline to up to week 160

Regeneron Pharmaceuticals, Inc.

#### CONFIDENTIAL

#### Safety Endpoints (Part A, B, and C):

- Incidence of treatment-emergent adverse events (TEAEs) during the 16-week doubleblind treatment period
- Incidence of TEAEs during the 36-week extended treatment period
- Incidence of TEAEs during the 108-week open-label extension period
- Incidence of treatment-emergent serious adverse events (SAEs) during the 16-week double-blind treatment period
- Incidence of treatment-emergent SAEs during the 36-week extended treatment period
- Incidence of treatment-emergent SAEs during the 108-week open-label extension period
- Incidence of treatment-emergent adverse events of special interest (AESIs) during the 16-week double-blind treatment period
- Incidence of treatment-emergent AESIs during the 36-week extended treatment period
- Incidence of treatment-emergent AESIs during the 108-week open-label extension period
- Incidence of TEAEs leading to permanent discontinuation of study treatment during the 16-week double-blind treatment period
- Incidence of TEAEs leading to permanent discontinuation of study treatment during the 36-week extended treatment period
- Incidence of TEAEs leading to permanent discontinuation of study treatment during the 108-week open-label extension period
- Incidence of treatment-emergent ADA responses and titer during the 16-week doubleblind, 36-week extended treatment periods, and 108-week open-label extension period

#### **Clinical Pharmacology Endpoint:**

Concentrations of functional dupilumab in serum by treatment regimen at each assessment time point from baseline to end of study

## 4.1.3. Exploratory Endpoints

The exploratory endpoints are:

- Proportion of patients achieving peak esophageal intraepithelial eosinophil count of ≤1 eos/hpf at week 16
- Percent change in total score of Pediatric EoE Impact Scale-caregiver version (PEIS-C) from baseline to week 16 (for caregivers of patients aged ≥1 to <12 years)

- Percent change in total PEIS-P (patient version) score from baseline to week 16 (for patients aged ≥8 to <12 years)

- Change in GIC-patient, caregiver, and clinician version score at up to week 52
- Change in GIS-patient, caregiver, and clinician version score from baseline to up to week 160/EOT
- Change from baseline in body weight for age percentile at week 16
- Change in body mass index for age z-score from baseline to week 16 for patients ≥2 years of age
- Change in weight for age z-score from baseline to week 16
- Change in weight for height z-score from baseline to week 16

# 5. STUDY VARIABLES

# 5.1. Demographic and Baseline Characteristics

Baseline characteristics will include standard demography (eg, age, sex, race, weight, height, etc.), EoE disease characteristics, medical history, and medication history for each patient.

## 5.2. Efficacy Variables

The efficacy variables include measurements or scores for individual patients of the following:

- From the endoscopy with EoE-EREFS and biopsies procedure: peak esophageal intraepithelial eosinophil counts, score of EoE-HSS (including EoE grade and stage scores), and score of EoE-EREFS
- Patient-, caregiver-, or clinician-reported outcomes:
  - score of the PESQ-P (for patients aged ≥8 to <12 years) and the PESQ-C (for patients aged ≥1 to <12 years)

  - score of the PEIS-P (for patients aged ≥8 to <12 years) and the PEIS-C (for caregivers of patients aged ≥1 to <12 years)

  - score of the GIC-P (for patients aged ≥8 to <12 years), GIC-C (for caregivers of patients aged ≥1 to <12 years), and GIC-Clin (for patients aged ≥1 to <12 years)

  - score of the GIS-P (for patients aged ≥8 to <12 years), GIS-C (for caregivers of patients aged ≥1 to <12 years), and GIS-Clin (for patients aged ≥1 to <12 years)

  - score of the PEESSv2.0- caregiver version (for patients aged  $\geq 1$  to <12 years)
- Measurement of body weight and height or length for patients <2 years of age; body mass index will be programmatically calculated based on weight and height/length data

# 5.3. Safety Variables

Safety variables include recording, measurements, or laboratory test results for individual patients of the following: adverse events (AEs); vital signs including heart rate, blood pressure, respiration rate, and body temperature; physical examination findings; results of laboratory tests including hematology, blood chemistry, urinalysis, and pregnancy test.

# 5.4. Pharmacokinetic Variables

The PK variable is the concentration of functional dupilumab in serum and time point for individual patients. These sampling timepoints are specified in Table 1, Table 2, Table 3, and Table 4.

## 5.5. Immunogenicity Variables

The immunogenicity variables are ADA status, titer, neutralizing antibody (NAb) status, and time point/visit. Samples in this study will be collected at the clinic visits specified in Table 1, Table 2, Table 3, and Table 4.

## 5.6. Pharmacodynamic and Other Biomarker Variables

Pharmacodynamic and biomarker variables include laboratory test results for individual patients of the following: serum total IgE and eotaxin-3.

# 6. STUDY DESIGN

# 6.1. Study Description and Duration

This is a phase 3, multicenter, randomized, 3-part, double-blind, placebo-controlled study investigating the efficacy, safety, tolerability, PK, and immunogenicity of dupilumab in pediatric patients (ages  $\geq 1$  to <12 years) with active EoE.

Approximately 90 patients will be randomized (1:1:1 ratio for higher exposure dupilumab group: lower exposure dupilumab group: placebo) at approximately 30 study sites globally. The dosing of the placebo group will be matched with higher exposure and lower exposure dupilumab regimens in the respective weight tiers and placebo with different dosing will be combined. The details on the randomization will be specified in an interactive voice/web response system (IVRS/IWRS) requirement document.

This study consists of a screening period of up to 85 days, a double-blind 16-week treatment period (Part A), a 36-week extended active treatment period (Part B), a 108-week open-label extension period (Part C) and a 12-week follow-up period. The open-label extension period (Part C) will add up to 108 weeks of open-label treatment or until dupilumab becomes commercially available in the country of the participating patients (whichever comes first).

The study flow diagram is provided in Figure 1.

#### Figure 1: Study Flow Diagram

After patients and their legal parents/legal guardians provide informed assent (as appropriate) and informed consent, patients will be assessed for study eligibility.

Patients who have completed their end of study (EOS) visit prior to amendment 4 will be reevaluated for eligibility at a Re-Entry visit for participation in the open-label extension period (Part C) and Safety Follow-up period (see Section 7.2.2.3). Patients who have entered the safety followup period after completing Part B at the time of amendment 4 approval may immediately enter the open-label extension (Part C) without being required to complete an EOS visit prior to entering Part C.

Patients are required to have a documented diagnosis of EoE which may be established either by a prior historical biopsy, as demonstrated by intraepithelial eosinophilic infiltration (peak eosinophils/high power field  $\geq$ 15 eos/hpf) (400×) from at least 1 esophageal region and performed after at least 8 weeks of treatment with an approved PPI regimen, or by biopsies performed after approximately 8 weeks of PPI treatment initiated prior to screening or during the screening period, which demonstrates  $\geq$ 15 eos/hpf) (400×) from at least 2 of the 3 esophageal regions (proximal, mid, and distal); if the PPI regimen is stopped, biopsies must occur within 2 weeks of stopping the PPI. See Figure 2 for endoscopy/biopsy procedure flow chart.

Regeneron Pharmaceuticals, Inc.

#### CONFIDENTIAL

#### Figure 2: Endoscopy/Biopsy Procedure Flow Diagram

\* Biopsy specimens from the antrum and duodenum will be obtained in all patients to rule out alternate etiologies. All randomized patients found to have stomach and/or duodenal abnormalities at baseline will have follow-up stomach and/or duodenal biopsies at week 16, week 52, week 100, and week 160.

Patients who are on PPIs during the screening period to rule out EoE disease management with this treatment, and are eligible to enroll in the study, have the choice either to remain on the PPI regimen during the entire study or stop the PPI regimen prior to baseline; they then must remain off of PPIs during the entire study.

Biopsies will be obtained by endoscopy at the screening visit 2, week 16 visit, week 52, week 100 and week 160 visits, or immediately prior to start of rescue medication or procedures (only applies to rescue medication and/or procedures that occur before the week 52 visit). A total of at least 9 mucosal pinch biopsies will be collected at each time point from 3 esophageal regions: 3 proximal, 3 mid, and 3 distal. Two samples from each region will be used for histology (needed for study inclusion criteria, as well as endpoint assessment) and the others for RNA extraction. Biopsies will be used for exploratory research to study EoE, dupilumab mechanism of action, and to identify or validate predictive biomarkers (efficacy and/or safety). Exploratory analyses of the biopsies may include but are not limited to immunohistochemistry [IHC] and RNA sequencing (or other methods for assessing RNA expression and RNAscope).

Regeneron Pharmaceuticals, Inc.

CONFIDENTIAL

Patients may be re-screened if they fail the Part A baseline screening evaluation, unless the reason for screen failure is related to histologic inclusion criteria. The baseline endoscopy with biopsies and EoE-EREFS scoring will not be repeated for re-screened patients. These results will continue to be valid baseline data. Re-screening must occur within 6 months of the screen failure.

Patients may receive concomitant medications (except for prohibited medications specified in Section 8.10.1) as needed, at the discretion of the investigator, while continuing study treatment. Frequency of use and type of product will be documented.

Efficacy, safety, laboratory assessments, and samples for assay of concentration of functional dupilumab in serum and potential ADA response to dupilumab, as well as research samples, will be performed or collected at specified time points throughout the study according to the Schedule of Events in Table 1, Table 2, Table 3, and Table 4.

NOTE: If there are restrictions to the clinical study as a result of the COVID-19 pandemic, it may be necessary to adjust the visit schedule, convert in-person visits to telephone contacts, and postpone study procedures until the next available in clinic study visit. It is necessary that the randomization visit (visit 3), the first visit of Part B and the first visit of Part C occur in the clinic. Endoscopies with biopsies are required at the visit 2 screening biopsy and at approximately week 16, week 52, week 100, and week 160. If it is not possible to complete the endoscopies with biopsies due to COVID-19 restrictions and provided there are no specific safety concerns for the patient, patients may continue their current study medication regimen until the endoscopies with biopsies can be performed. All temporary mechanisms utilized, and deviations from planned study procedures in response to COVID-19 are to be documented as being related to COVID-19 and will remain in effect only for the duration of the public health emergency. Once COVID-19 conditions resolve, all study visits and procedures should follow the schedule of events.

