#### 7.2.2. Exclusion Criteria

#### 7.2.2.1. Exclusion Criteria for Part A - Double-Blind Treatment

A patient who meets any of the following criteria will be excluded from the study:

- 1. Body weight <5 kg or  $\ge60$  kg at screening
- 2. Prior participation in a dupilumab clinical trial or past or current treatment with dupilumab
- 3. Initiation or change of a food-elimination diet regimen or re-introduction of a previously eliminated food group in the 6 weeks prior to screening. Patients on a food-elimination diet must remain on the same diet throughout the study.
- 4. Other causes of esophageal eosinophilia or the following conditions: eosinophilic gastroenteritis, hypereosinophilic syndrome, and eosinophilic granulomatosis with polyangiitis (Churg-Strauss syndrome)
- 5. Active Helicobacter pylori
- 6. Helminthic infection
- 7. History of Crohn's disease, ulcerative colitis, celiac disease, or prior esophageal surgery
- 8. Any esophageal stricture unable to be passed with a standard, diagnostic, upper endoscope or any critical esophageal stricture that requires dilation at screening
- 9. Treatment with swallowed topical corticosteroids within 8 weeks prior to baseline standard of care endoscopy
- 10. Treatment with subcutaneous immunotherapy (SCIT) unless on a stable maintenance dose for at least 1 year
- 11. Prior treatment with sublingual immunotherapy (SLIT), epicutaneous immunotherapy (EPIT), or oral immunotherapy (OIT)
- 12. Initiation, discontinuation, or change in the dosage regimen of the following medications within 8 weeks prior to the baseline endoscopy: PPIs, leukotriene inhibitors, and nasal and/or inhaled corticosteroids
- Treatment with systemic immunosuppressant/immunomodulating drugs, including but not limited to systemic corticosteroids, mepolizumab, omalizumab, cyclosporine, mycophenolate-mofetil, interferon-gamma (IFN-γ), Janus kinase inhibitors, azathioprine, and methotrexate within 3 months prior to screening
  - a. NOTE: One-time use of a corticosteroid as a part of the anesthetic preparation used during each endoscopy procedure is allowed.
- 14. Treatment with an investigational drug within 2 months or within 5 half-lives (if known), whichever is longer, prior to baseline visit

- 15. History of bleeding disorders or esophageal varices that, in the opinion of the investigator, would put the patient at undue risk for significant complications from an endoscopy procedure

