## 8.10. Concomitant Medications and Procedures

Any treatment administered from the time of informed consent/assent to final study visit will be recorded. Any treatment administered from the time of first dose of study drug to the final study visit will be considered concomitant treatment. This includes medications that were started before the study and are ongoing during the study.

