### 9.1.1. Footnotes for the Schedule of Events Tables

#### 9.1.1.1. Footnotes for Table 1

- 1. For patients without a satisfactory prior endoscopy/biopsy (eg, histological criteria were not met, or the biopsy was not performed while patient was on at least 8 weeks of PPI treatment), the screening period will be extended for up to 12 weeks (day -85) to allow for at least 8 weeks of PPI treatment prior to the screening endoscopy/biopsies. For all other patients, the screening period will be shorter, with sufficient time to allow screening assessments and laboratory test results to be available prior to the baseline endoscopy/biopsies.
- 2. The endoscopy/imaging for EoE-EREFS/biopsy procedures should be performed after all other efficacy and safety assessments.

2a. The baseline esophageal endoscopy with biopsies and the stomach and/or duodenum endoscopies with biopsies should be performed with sufficient time to allow for availability of the intraepithelial eosinophil count result from the central pathology laboratory prior to day 1. For patients without a satisfactory prior historical endoscopy/biopsy, the baseline endoscopy/biopsies must be performed after at least 8 weeks of PPI. Patients may be randomized as soon as their endoscopy/biopsy results are confirmed, and all other eligibility criteria are met.

2b. For patients who receive rescue treatment during the double-blind treatment period, the endoscopy/EoE-EREFS/biopsy procedures will be performed prior to the initiation of rescue treatment. Patients undergoing endoscopy/biopsy prior to rescue will not undergo the subsequent scheduled endoscopy/biopsy at week 16 and/or week 52.

- 3. Patients may be re-screened if they fail the screening evaluation, unless the reason for screen failure is related to histologic or clinical disease severity inclusion criteria. The baseline endoscopy with biopsy and EoE-EREFS scoring will not be repeated for rescreened patients. These results will continue to be valid baseline data. Re-screening must occur within 6 months of the screen failure.
- 4. Assessments indicated for this week 16 (end of treatment) visit should be performed for all patients. For patients who will enter extended treatment, there are additional events listed for the week 16 visit in Table 2.
- 5. Patients and/or caregivers will be trained on administration of study drug.

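### A re-screened child keeps the old endoscopy as baseline, with nothing to rule out an elimination diet or swallowed-steroid course begun in between

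*Protocol*

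**What the plan says.** Section 6.1 (text after Figure 2) allows re-screening after a Part A screen failure unless the failure was histologic. On the endoscopy it states: "The baseline endoscopy with biopsies and EoE-EREFS scoring will not be repeated for re-screened patients. These results will continue to be valid baseline data". The time limit is: "Re-screening must occur within 6 months of the screen failure". Table 1 footnote 3 (section 9.1.1.1) gives the same reuse rule and the same 6 months.

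The rules on earlier treatment are in section 7.2.2.1:
- Exclusion 9: "Treatment with swallowed topical corticosteroids within 8 weeks prior to baseline standard of care endoscopy".
- Exclusion 12 (PPIs, leukotriene inhibitors, nasal or inhaled steroids) is also tied to the 8 weeks before the baseline endoscopy.
- Exclusion 3 bars starting or changing an elimination diet, or "re-introduction of a previously eliminated food group in the 6 weeks prior to screening". It then requires a child on such a diet to stay on it.
- Exclusion 13 bars systemic steroids and immunosuppressants in the 3 months before screening.

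On-study restrictions begin later. Section 8.10 states: "Any treatment administered from the time of first dose of study drug to the final study visit will be considered concomitant treatment".

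The two re-screening bars are not the same. Section 6.1 names histologic failure only. Footnote 3 allows re-screening "unless the reason for screen failure is related to histologic or clinical disease severity inclusion criteria".

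**The concern.** Tying the steroid and PPI windows to the endoscopy works when biopsy and randomisation fall in one short screening period. Once the biopsy is carried across a screen failure, the same windows leave an interval in which the child may be treated for EoE and still meet inclusion 3 on the old slides.

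That biopsy does several jobs. It is the histologic entry condition. It is the reference for percent change in peak eosinophils and for change in EoE-HSS, EoE-EREFS and the transcriptome scores at weeks 16, 52, 100 and 160. It supplies the baseline covariate in the ANCOVA. It can also be the imputed value where a once-measured week 16 result is missing (section 11.4.3.2). If it is out of date, all of these are wrong for that child. If the child is already at or below 6 eos/hpf and remains so, the child can be a primary-endpoint responder without any drug effect.

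**Working it through.** **1. Age of the reused biopsy.** The inputs are 6 months, taken as 183 days (section 6.1), and the time from endoscopy to failure plus the time from re-screening to day 1. Footnote 1 reserves the long, 85-day screening for children who need at least 8 weeks of PPI before endoscopy, which leaves about 85 − 56 = 29 days after it. For everyone else screening is shorter, with no figure given. I assume 28 days at each end.
- Lower end, negligible screening time: 0 + 183 + 0 = 183 days, about 6 months.
- Upper end: 28 + 183 + 28 = 239 days, 239 / 7 = 34 weeks, about 8 months.

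Both apply to a child who uses the full 6 months; an earlier return shortens the gap.

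**2. What covers the interval from the old endoscopy to visit 3.**

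| Rule | Anchor | Reach into the interval |
|---|---|---|
| Exclusion 9, swallowed steroids | 8 weeks before endoscopy | None |
| Exclusion 12, PPI and others | 8 weeks before endoscopy | None |
| Exclusion 3, diet | 6 weeks before screening | The 6 weeks before re-screening, if screening means the new one |
| Exclusion 13, systemic drugs | 3 months before screening | The 3 months before re-screening, same proviso |
| Exclusion 16 | Planned use during the study | Not a course finished before day 1 |
| Section 8.10.1, diet change | During study treatment | None |
| Inclusion 4, symptoms | Month before screening | Tests symptoms, not histology |

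**3. Two routes that pass.** The child has a qualifying biopsy and then fails on, for example, an infection (the note to exclusion 20 expressly allows re-screening) or too few diary days (inclusion 5).
- *Diet.* An elimination diet starts after the biopsy and more than 6 weeks before re-screening. Exclusion 3 is satisfied, and its second sentence then holds the diet in place through week 16. The introduction puts non-resolution on diet at 30% to 40%, so remission is a realistic outcome.
- *Swallowed steroid.* A course is given after the biopsy and completed before day 1. No criterion mentions it.

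In either route inclusion 4 must still be met, so the child must have EoE symptoms reported in the month before screening.

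**4. Illustrative size.** The plan's own figure is 95% power with 30 per arm, 5.1% against 40.7%, two-sided 5% Fisher's exact test. Full enumeration gives 90.1%. That is a separate matter, and I use 90.1% only as the reference here.

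Let a fraction f of each arm enter in remission and all remain so at week 16:
- placebo = 0.051 + f × (1 − 0.051)
- dupilumab = 0.407 + f × (1 − 0.407)
- difference = 0.356 × (1 − f)

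With f = 2/30 = 0.0667:
- placebo = 0.051 + 0.0667 × 0.949 = 0.114
- dupilumab = 0.407 + 0.0667 × 0.593 = 0.447
- difference = 0.356 × 0.9333 = 0.332

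In the power range below, the lower figure assumes every remission lasts in both arms. The upper assumes half last on placebo and all count as responders on dupilumab.

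| Children per arm entering in remission | Power |
|---|---|
| 0 | 90.1% |
| 1 | 83.8% to 89.0% |
| 2 | 77.3% to 88.0% |
| 3 | 70.7% to 87.3% |

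The document gives no count for the first column.

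**5. The two re-screening bars.** Section 7.2.1 has no criterion labelled clinical disease severity; the nearest is the symptom history in inclusion 4. Under section 6.1 a child who fails inclusion 4 may be re-screened. Under footnote 3 a site may reasonably refuse.

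**The case against.** Several stronger readings are tempting, and the document does not support them.

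- *The biopsy could be almost a year old.* Adding two full screening periods gives 85 + 183 + 85 = 353 days. Footnote 1 makes this unrealistic: the long screening exists to fit PPI treatment before the endoscopy, and a child who already has a valid biopsy gets the shorter one.
- *PPI remission in about half of patients.* The introduction gives that rate for EoE generally. These children had at least 15 eos/hpf after at least 8 weeks of PPI, and section 3.2.1 describes them as histologically non-responsive. A PPI change in the interval is unrestricted, but it is a weak route to remission.
- *Such a child is a responder in any arm.* Only if remission lasts. Swallowed steroids are prohibited on study, and starting them makes the child a non-responder. The introduction itself notes relapse once standard therapy stops. The diet route is stronger because the diet must continue.
- *Any screen failure opens the gap.* Laboratory failures should normally precede the endoscopy (footnote 1, inclusion 2). Infection and diary failures can be corrected quickly, so a return near 6 months is an extreme case.
- *The Part A result is in doubt.* Randomisation balances such children in expectation, so the primary comparison is diluted rather than tilted towards dupilumab. Sections 1 and 3.3.1.1 report that both regimens met the primary endpoint with p < 0.0001.

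Inclusion 4 and exclusions 13 and 16 are real but partial safeguards. It is also fair that new entry wording cannot change a completed enrolment. None of this removes the gap itself: reuse is unconditional, and no rule covers diet or swallowed steroids across the whole interval.

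**Conclusion.** The point stands in a limited form. The protocol lets a child be randomised on an endoscopy that may be roughly 6 to 8 months old, after a change of diet or a swallowed-steroid course that no criterion detects. The upper end rests on my assumed 28-day screening intervals.

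There are two consequences. The week 16 difference is diluted if remission persists: 35.6 to 33.2 points with 2 of 30 per arm, an illustration and not an estimate. Change-from-baseline values based on endoscopy are false for such a child at weeks 16, 52, 100 and 160. The later time points have no placebo comparator, so improvement that predates randomisation would be read there as improvement on treatment. How many children were re-screened, and how many were treated in the interval, is unknown, so the actual effect may be nil.

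The mismatch between section 6.1 and footnote 3 is a plain inconsistency, whatever those numbers are.

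**What to change.** 1. In section 6.1 and Table 1 footnote 3, let the old endoscopy count as baseline only if the diet and treatment conditions of exclusions 3, 9 and 12 also hold from that endoscopy to visit 3. In both places, except the PPI stop before baseline that sections 6.1 and 8.2 already allow. A child who does not meet this is not re-screened; no repeat biopsy is needed. The cost is wording in two places, one eligibility check and the loss of a few re-screened children.

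2. Part A enrolment is complete, so the practical remedy is in the analysis. From recorded medication and diet data, identify every randomised re-screened child with such a change between the reused endoscopy and visit 3, and report the number by arm. Add a sensitivity analysis of the primary and the endoscopy-based change-from-baseline endpoints excluding them. The flag uses only pre-randomisation information, so the comparison among the remaining children is still randomised. Define it without reference to outcome, and label the analysis as added after the Part A results. If the interval between failure and re-screening was not fully recorded, say so. The cost is one data review and one extra set of tables.

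3. Reconcile the re-screening bar in section 6.1 with footnote 3, use one wording in both, and cite inclusion criteria by number so that the status of an inclusion 4 failure is clear. This costs only an edit.
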